**\* At the discretion of the Investigator, laboratory values can be confirmed with a second assessment. In this case, only the result of the second assessment will be considered valid and final.**

Adverse events occurring after Study Day 28 will not be considered DLTs, however, they may be considered in further decisions regarding the number of patients to enroll in a given dosing cohort. If a patient is not followed for the 28-day period following Study Day 1 due to discontinuation, for reasons other than DLTs, or if, from Study Day 1 through Study Day 28, a patient misses  $> 6$  consecutive doses of treatment or  $> 20\%$  of the planned study drug doses, another patient will be enrolled into that dose level and stratum. For toxicities which, by definition, require a time-window for them to be defined as DLTs (grade 3 non-hematologic toxicity for  $\geq$  7 consecutive days) a subsequent visit(s) and/or laboratory assessment(s) must be scheduled accordingly, in order for this toxicity to qualify as a DLT. A minimum of 9 evaluable patients from each stratum (stratum 1 consists of patients with baseline PLT counts  $75-99 \times 10^9/L$  and stratum 2 consists of patients with baseline PLT counts  $50-74 \times 10^9/L$ ) must be treated at the dose declared to be the MSSD.

Enrollment of patients and dose escalation will be performed as described in [Section 5.1.2.1](#), [Section 5.1.2.2](#), [Section 5.1.2.3](#) and [Section 5.1.2.4](#).

Intra-patient escalation during the dose escalation phase of the study will be allowed according to the rules described in the [Section 5.1.2.6](#).

[figure not shown]
Following determination of the MSSD, a safety expansion phase will be conducted. Patients from both strata can be enrolled simultaneously during the safety expansion phase, allocated to a dose equal to the respective MSSD for their stratum. If the MSSD is the same in both strata, all patients in the safety expansion phase will be treated with the same dose, regardless of the baseline PLT counts.

In the safety expansion phase, the safety and tolerability of the MSSD will be further evaluated with the purpose of establishing that this dose is suitable for use in the low-platelet population of patients with MF. The Bayesian logistic regression model (BLRM) with escalation with overdose control (EWOC) will continue to be updated with data from patients participating in the safety expansion phase.

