**Table 5-3 Criteria for defining dose-limiting toxicities**

Toxicity	Any of the following treatment-related criteria (occurring through Study Day 28)
Hematology	PLT counts $< 25 \times 10^9/L$ * grade 4 neutropenia ( $ANC < 0.5 \times 10^9/L$ )* grade $\geq 3$ febrile neutropenia*
Other AEs	any grade thrombocytopenia requiring PLT transfusion any grade $\geq 2$ hemorrhagic event grade $\geq 2$ serum bilirubin with coincident direct bilirubin $\geq 0.5$ mg/dL grade 3 non-hematologic toxicity for $\geq 7$ consecutive days grade 4 non-hematologic toxicity

\* At the discretion of the Investigator, laboratory values can be confirmed with a second assessment. In this case, only the result of the second assessment will be considered valid and final.

Patients who experience a DLT will have their therapy with INC424 interrupted and will be followed as described in the [Table 5-4](#). After recovery from the toxicity in question, if the Investigator believes that it is in the patient's best interest to resume therapy with INC424, the patient may resume therapy, only after consultation with the Sponsors, according to the guidelines described in the [Section 5.1.3](#) and the [Table 5-4](#).

However, the patient must be permanently discontinued from study medication and withdrawn from the study, if **any** of the following DLTs occur:

- any grade  $\geq 3$  hemorrhagic event
- 2nd episode of grade  $\geq 3$  febrile neutropenia
- grade 3 renal toxicity for  $\geq 7$  consecutive days
- grade 4 renal toxicity

- grade 4 serum bilirubin with direct bilirubin  $\geq 0.5$  mg/dL
- grade 4 non-hematologic toxicity

If, from Study Day 1 through Study Day 28, a patient misses  $> 6$  consecutive doses of treatment or  $> 20\%$  of the planned study drug doses, the patient will not be evaluable for DLTs. The patient can continue in the study, but another patient has to be enrolled at the same dose level and stratum in order to reach the required number of patients in the cohort.

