#### **6.1.4.1 Replacement policy**

Patients withdrawn from the study will not be replaced.

However, if, from Study Day 1 through Study Day 28, a patient misses > 6 consecutive doses of treatment or > 20% of the planned study drug doses, the patient can continue in the study without being evaluable for DLTs. Consequently, another patient has to be enrolled into the same dose level and stratum in order to reach the required number of patients in the cohort.

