### **9.1.3 Dose-determining Set**

The Dose-determining Set (DDS) consists of all patients from the safety set who either (i) meet the minimum exposure criterion and have sufficient safety evaluations as defined below, or (ii) discontinue due to DLT. The patients in the DDS enrolled in the dose-finding part of the study will be the patients used for determination of the MSSD.

A patient is considered to have met the minimum exposure criterion and to have had sufficient safety evaluations if they have not missed > 20% of the planned doses and no more than 6 consecutive doses in the first 28 days, and have completed all required safety evaluations through Study Day 28.

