2.1 Definitions for subjects and treatments

2.1.1 Analysis sets

Full Analysis Set (FAS) comprises all patients who received at least one dose of study medication.

Safety Set includes all patients who received at least one dose of study medication.

Note that the patient population for both FAS and Safety Set are the same.

Dose-determining Set (DDS) consists of all patients from the Safety Set who either (i) meet the minimum exposure criteria and have sufficient safety evaluations as defined below, or (ii) experience a DLT. The patients in the DDS enrolled in the dose-finding part of the study will be the patients used for determination of the MSSD.

Note: this is a clarification to the definition of the DDS in Section 9.1.3 of the protocol. The DDS contains all patients who experienced a DLT regardless of whether they permanently discontinued treatment as Section 5.1.2.8 defines circumstances where patients who experienced a DLT can resume treatment.

A patient is considered to have met the minimum exposure criteria and to have had sufficient safety evaluations if they have not missed > 20% of the planned doses and no more than 6 consecutive doses in the first 28 days, and have completed all required safety evaluations through Study Day 28.

Patients in the DDS will be identified based on the list of evaluable patients used for determination of the MSSD, as well as the VAP M3 Protocol Deviations. Patients with protocol deviation code 18 (indicating exclusion from dose-finding population) will be excluded from DDS.

Patients will be analyzed by stratum and for each stratum, patients will be categorized according to the first dose level they received. Patients will be categorized the following way: (1) Group 1, including patients with starting dose of 5mg AM + 5mg PM or 5mg AM + 10mg PM; (2) Group 2, including patients with starting dose of 10mg AM + 10mg PM; (3) Group 3, including patients with starting dose of 10mg AM + 15mg PM or 15mg AM + 15mg PM. Such categorization depends on the highest dose level being reached in each stratum. For example, the highest dose level reached in Stratum 2 is 10mg AM + 10mg PM, so there will be only two groups for Stratum 2: (1) Group 1, including patients with starting dose of 5mg AM + 5mg PM or 5mg AM + 10mg PM; (2) Group 2, including patients with starting dose of 10mg AM + 10mg PM.

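### The protocol's missed-dose rule has no exception for doses held because of a DLT, and the SAP corrects the definition but not the step that identifies the dose-determining set

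*Protocol*

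**What the plan says.** **The hold.** Protocol 5.1.2.8: "Patients who experience a DLT will have their therapy with INC424 interrupted". The patient may resume after recovery, unless the event is on that section's list requiring permanent discontinuation.

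**The missed-dose rule.** The same section ends with the rule that a patient who, from Study Day 1 to 28, "misses $> 6$ consecutive doses of treatment or $> 20\%$ of the planned study drug doses, the patient will not be evaluable for DLTs". Another patient must then be enrolled at that dose level and stratum. Protocol 6.1.4.1 repeats it: "the patient can continue in the study without being evaluable for DLTs". Protocol 3.1 gives the replacement condition as "due to discontinuation, for reasons other than DLTs, or if, from Study Day 1 through Study Day 28, a patient misses" more than the limits. There the DLT exception qualifies discontinuation, not missed doses.

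**The analysis set.** Protocol 9.1.3 admits to the DDS patients who meet the exposure criterion and have sufficient safety evaluations, "or (ii) discontinue due to DLT". Protocol 5.1.2.4 uses the same two limbs.

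**The SAP.** SAP 2.1.1 rewrites limb (ii) as experiencing a DLT, and says that this covers patients who did not stop permanently, because 5.1.2.8 lets some resume. The document history logs the change under 27 Nov 2017. The same section then identifies DDS patients from the list of evaluable patients used for the MSSD, together with the protocol-deviation document, and adds: "Patients with protocol deviation code 18 (indicating exclusion from dose-finding population) will be excluded from DDS".

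**The concern.** The exclusion is triggered by the outcome that the model estimates. A DLT leads to a mandatory hold. A hold of sufficient length makes the patient non-evaluable, and the replacement is a fresh patient who may have no DLT. The effect runs one way: the observed DLT rate falls, the posterior overdose probability falls, and the model favours higher doses. The DDS carries the primary endpoint and the MSSD, and a platelet count below 25 x 10^9/L is a DLT that Table 5-4 manages by a hold.

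The SAP's rewording ought to end the matter, but two things keep it open. It is dated after both MSSDs had been declared; the Amendment 4 rationale of 2015 already gives 15 mg BID for Stratum 1 and 10 mg BID for Stratum 2. And its operational step starts from a list drawn up while the protocol wording applied. If a DLT patient was left off that list, or carries code 18, the listed set would contradict the definition a few lines above it.

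**Working it through.** **1. Which DLT patients the rule reaches.** Dosing is twice daily (protocol 5.1.2), so Days 1-28 hold 2 x 28 = 56 planned doses.
- More than 6 consecutive doses: tripped at 7 doses, or 3.5 days.
- More than 20%: 0.20 x 56 = 11.2, tripped at 12 doses, or 6 days.
- The latest start for a hold that runs to the end of Day 28 and trips the rule is the evening dose of Day 25: 1 + 2 x 3 = 7 doses.
- A hold from the morning of Day 15 (a haematology visit in Table 6-1) to the end of Day 28 misses 2 x 14 = 28 doses.

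Not reached: DLTs that begin later, shorter holds, and DLTs that lead to permanent discontinuation, which limb (ii) already covers.

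**2. Where such a patient falls.**

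| Text | DLT patient held past the limits who resumes |
|---|---|
| Protocol 3.1, 5.1.2.8, 6.1.4.1 | Not evaluable; another patient enrolled |
| Protocol 5.1.2.4, 9.1.3 limb (i) | Fails on exposure |
| Protocol 5.1.2.4, 9.1.3 limb (ii) | Fails; did not discontinue |
| SAP 2.1.1, definition | In the DDS |
| SAP 2.1.1, identification step | Depends on the MSSD list and code 18 |

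**3. Size of the bias in the rate.** If a share h of DLT patients is dropped and replaced, the rate observed among evaluable patients is p(1 - h)/(1 - ph). The documents do not give h, so these values are assumptions.

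| True rate p | h = 0.25 | h = 0.50 | h = 0.75 |
|---|---|---|---|
| 0.33 | 0.27 | 0.20 | 0.11 |
| 0.25 | 0.20 | 0.14 | 0.08 |

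For example, 0.33 x 0.5 / (1 - 0.165) = 0.20.

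**4. Effect on the model's decision.** Inputs are from protocol Table 9-1 and 9.4.2:
- log(alpha) and log(beta) from a 0.9/0.1 mixture of bivariate normals. The first has means -1.010, -0.259, SDs 0.876, 0.918 and correlation -0.103. The second has means -1.447, -0.385, SDs 1.095, 1.412 and correlation -0.065.
- gamma normal with mean log(1.5) and SD 0.354; reference dose 30 mg/day.
- logit(pi) = log(alpha) + beta x log(d/30) + gamma x I(stratum 2).
- A dose is admissible if P(pi >= 0.33) < 0.25.

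Method: Monte Carlo draws from the prior, weighted by the binomial likelihood.

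The plan's own figures come first. The prior probabilities and means in Table 9-1 reproduce within 0.004 (Stratum 1, 20 mg/day, excessive toxicity: 0.220 against the stated 0.221). The nine Stratum 1 situations checked in Table C of Appendix 13 give the stated recommendations.

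Then Stratum 1, with one DLT patient dropped and replaced by a patient without a DLT:

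| Data | Quantity | All DLTs counted | One DLT lost |
|---|---|---|---|
| 0/3 at 10, 0/3 at 15, then 2/3 or 1/3 at 20 mg/day | P(pi >= 0.33) at 25 | 0.31, barred | 0.13, admissible |
| 0/3 at 10, then 2/3 or 1/3 at 15 mg/day | P(pi >= 0.33) at 15 | 0.29, barred | 0.10, admissible |
| 0/3 at each lower dose, then 4/9 or 3/9 at 30 mg/day | P(pi >= 0.33) at 30 | 0.27, barred | 0.13, admissible |
| 0/3 at 10, 0/3 at 15, then 1/3 or 0/3 at 20 mg/day | P(pi >= 0.33) at 25 | 0.13, admissible | 0.04, admissible |

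In the second row with one DLT lost, 20 mg/day also becomes admissible (0.167). The last row shows that a lost DLT does not always matter. The first three rows lie close to the 0.25 limit. All are hypothetical data.

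**The case against.** The strongest answer is that the current SAP already states the right rule: its DDS contains every patient who experienced a DLT, and the DLT summaries use that set. This stands. A reader might infer that true DLTs are excluded from the planned final analysis; on the SAP's definition they are not. The code 18 route is a possibility, since neither the list nor the deviation document is available to show that it removes anyone.

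Several protocol passages also suggest that exclusion was never intended. Table 5-4 marks held events as DLTs and then describes resumption, while its footnotes calling for substitution sit only under non-treatment-related toxicity. Section 5.1.1 speaks of a missed dose as one the patient forgot. Sections 5.1.2.4 and 9.4.2 re-evaluate the model when two patients experience a DLT, whether or not they stop. Section 5.1.2.8 says that DLTs enter the model. These are good evidence of intent, but none of them amends the evaluability or replacement sentences.

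A reader might also infer that DLTs were lost and that the declared MSSDs are too high. The documents do not show this. The only conduct evidence, the Amendment 3 study status, reports a thrombocytopenia DLT in Stratum 2 at 10 mg BID that led to cohort expansion; it does not say whether that patient resumed. The model is also one input among several. Protocol 5.1.2.3 puts all clinical, laboratory and toxicity data before the dose-escalation meeting, so a DLT patient outside the DDS would still be seen there. Finally, the MSSDs are declared and Amendment 4 moved new Stratum 1 patients to 10 mg BID, so the remedy lies mainly in the final analysis and report.

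**Conclusion.** The point holds as an inconsistency in analysis-set membership. Read as written, the protocol omits and replaces a DLT patient who is held for at least 7 consecutive or 12 total doses in Days 1-28 and then resumes. The bias is downward. The SAP repairs the definition but leaves an identification step that can undo it.

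The size cannot be fixed from the documents, because the share of DLT patients affected is not given. With an assumed share of 0.25 to 0.75, a true rate of 33% would appear as 27% to 11%. One lost DLT reverses the model's decision only near the overdose boundary, as in 0.31 versus 0.13 at 25 mg/day. This assumes that the replacement has no DLT and that the meeting follows the model. No actual loss is shown. The correction is still worth making, because it is cheap and bears on the primary endpoint.

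**What to change.** 1. In protocol 3.1, 5.1.2.8 and 6.1.4.1, state that the missed-dose rule for evaluability and replacement applies only to patients without a DLT. Align limb (ii) in 5.1.2.4 and 9.1.3 with SAP 2.1.1.
2. In SAP 2.1.1, state that neither the MSSD evaluable list nor code 18 can remove a patient who had a DLT.
3. Re-derive DDS membership from the DLT and dosing data. List in the study report any DLT patient left out of previous model runs, or state that there were none.
4. Produce the final table of posterior DLT probabilities (SAP 2.3.1) on that set.

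This concerns analysis-set membership only; no change to dose holds or restarts is proposed. The cost is a few sentences, one re-derivation and one model run. The reported DLT rate may become slightly less favourable.

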### **5.1.2.9 Follow-up for dose-limiting toxicities**

Patients whose treatment is discontinued or interrupted due to a DLT, must be followed until resolution or stabilization of the DLT event, whichever comes first, as described in [Section 6.1.4](#).

In the case of PLT transfusion that is considered unrelated to the treatment with INC424 (e.g., car accident causing bleeding and subsequent PLT transfusion despite grade  $\leq 3$  thrombocytopenia), then no measures should be taken, other than those related to the management of the event ([Table 5-4](#)). If the event for which the PLT transfusion was given is considered related to the treatment with INC424, then both the PLT toxicity-handling guidelines and the hemorrhagic event-handling guidelines should be taken into account.

In case of a hemorrhagic event of any grade (CTCAE grade 1 included) the Investigator is advised to perform coagulation tests and albumin assessment.

#### **5.1.2.9.1 Hematologic toxicity**

- In the case of grade 4 thrombocytopenia, assessment of PLT count is recommended to be repeated daily, Monday through Friday, until resolution to grade  $\leq 3$  thrombocytopenia (it is at the Investigator's discretion to perform PLT count assessments during weekends). The subsequent follow-up should be done as described in [Section 5.1.4](#) and in [Table 6-2](#).
- In the case of grade 4 neutropenia, assessment of ANC count is recommended to be repeated at least twice a week until resolution to grade  $\leq 3$  neutropenia. The subsequent follow-up should be done as described in [Section 5.1.4](#) and in [Table 6-2](#) and [Table 6-4](#).

### **5.1.3 Dose modification and dose delay**

All dose modifications should be based on the worst preceding toxicity. Patients may be allowed dose reductions to 5 mg qd (dose level (-1)). Dose reductions more than one level at a time will not be allowed, except for thrombocytopenia, in which case different rules for dose reductions apply ([Table 5-4](#)). Note that the maximum allowed doses are quoted in the part of [Table 5-4](#) where guidelines for dose reduction due to thrombocytopenia are provided; lower doses may be used at investigator discretion. It is recommended that patients who are dose reduced for thrombocytopenia have more frequent hematology assessments. PLT counts must be obtained at least weekly for 4 weeks, and then at least every second week for the next 4 weeks. Thereafter, they may resume monthly evaluations.

Recovery of platelet counts will allow dose increases according to the guidelines in [Table 5-5](#). Note that once a dose is re-escalated, any subsequent declines in platelet count will require that [Table 5-4](#) be used to determine the new lower dose, or dose interruption.

Dose level (-1) is the lowest acceptable dosing level for a patient participating in the study. If a patient cannot tolerate dose level (-1), then he/she must be discontinued from study medication and withdrawn from the study (see [Table 5-2](#) for dose level definitions).

Dose modifications for toxicities occurring during the DLT-definition period (Study Day 1 through Study Day 28), and considered as treatment-related, will **not** be allowed until the toxicity qualifies as a DLT. After a toxicity event has been characterized as a DLT, a patient can resume therapy with a reduced INC424 dose according to the guidelines provided in the [Section 5.1.2.7](#). Dose modification recommendations after Study Day 28 are described in the [Table 5-4](#).

Any dose modifications must be recorded on the Dosage Administration Record eCRF.

#### **5.1.4 Treatment interruption and treatment discontinuation**

Patients may continue treatment with INC424 for the duration of the study or until they experience unacceptable toxicity that precludes any further treatment, disease progression, and/or at the discretion of the Investigator. Patients will be discontinued from the study if they withdraw consent, or if the treating physician judges that further therapy with INC424 is no longer in the patient's best interest.

Criteria for interruption and re-initiation of INC424 treatment are summarized in the [Table 5-4](#). A patient must discontinue treatment with INC424 if, after treatment is resumed at a lower dose, the same toxicity recurs with the same or worse severity. If a patient requires a dose delay of > 28 days, then the patient must be discontinued from the study. Patients who discontinue from the study for a treatment-related adverse event or a treatment-related abnormal laboratory value must be followed as described in [Section 6.1.4](#).

Grading of toxicity will be according to CTCAE Version 4.03.

Doses may be restarted and subsequently increased, according to the [Table 5-6](#), provided that platelet counts recover to  $\geq 35 \times 10^9/L$  and ANC counts recover to  $\geq 0.75 \times 10^9/L$  and there is no other toxicity that precludes dosing of the patient. Note that once a dose has been restarted, subsequent declines in platelet or ANC count will require that [Table 5-4](#) be used to determine the new lower dose or dose interruption. It is required that patients who have restarted dosing have more frequent hematology assessments. PLT and ANC counts must be obtained at least weekly for 4 weeks, and then at least every second week for the next 4 weeks. Thereafter, they may resume monthly evaluations (exception: for grade 4 thrombocytopenia or neutropenia events please refer to [Section 5.1.2.9.1](#)).

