#### **6.1.4 Discontinuation of Study Treatment/ Study**

Patients may voluntarily discontinue from study treatment and from the study for any reason at any time. If a patient decides to discontinue from the study treatment/ study, the investigator should make a reasonable effort (e.g., telephone, e-mail, letter) to understand the primary reason for this decision (or as per local regulation) and record this information in the patient's chart and on the appropriate eCRF pages. Patients may be considered withdrawn if

they state an intention to withdraw, fail to return for visits, or become lost to follow-up for any other reason.

The investigator should discontinue study treatment and discontinuation from the study for a given patient if he/she believes that continuation would be detrimental to the patient's well-being.

Study treatment must be discontinued and study participation ended under the following circumstances:

- Emergence of the following treatment related adverse events or lab abnormalities (see [Section 5.1.2.8](#) and [Table 5-4](#)):
  - Grade 3 or 4 hemorrhagic event of any kind
  - Second episode of grade  $\geq 3$  febrile neutropenia ( $ANC < 1.0 \times 10^9/L$ , with a single temperature of  $\geq 38.3^{\circ}C$  or a sustained temperature of  $\geq 38^{\circ}C$  for more than one hour)
  - Grade 3 renal toxicity for  $\geq 7$  consecutive days
  - Grade 4 renal toxicity
  - Grade 4 serum bilirubin with direct bilirubin  $\geq 0.5 \text{ mg/dL}$
  - Grade 4 non-hematologic toxicity
  - Grade 4 serum creatinine related to treatment from Day 1 to Day 28
  - Second episode of grade 3 or 4 serum creatinine from Study Day 29
  - Grade 4 other adverse event
  - Platelet counts reduce  $< 25 \times 10^9/L$  while taking INC424 at 5mg qd
- Pregnancy
- The following deviations from the prescribed dose regimen:
  - Interruption of study treatment for  $> 28$  days regardless of reason
  - If after 2 dose reductions and after the treatment has resumed at the lower dose, the same toxicity recurs with the same or worse severity (except for thrombocytopenia, anemia, and neutropenia)
  - If a patient cannot tolerate dose level (-1) (5 mg qd), which is the lowest acceptable dosing level for this study.

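### Protocol Sections 5.1.4 and 6.1.4 set different mandatory stops when a toxicity recurs after a lower-dose restart, and no text says which governs

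*Protocol*

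**What the plan says.** Two sections of the current protocol require treatment to stop when a toxicity comes back after a restart at a lower dose.

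- **Section 5.1.4:** the patient "must discontinue treatment with INC424 if, after treatment is resumed at a lower dose, the same toxicity recurs with the same or worse severity". The sentence names no minimum number of reductions beyond the one that produced the lower dose, and no exempt toxicity.
- **Section 6.1.4:** under the lead-in "Study treatment must be discontinued and study participation ended under the following circumstances", one bullet reads "If after 2 dose reductions and after the treatment has resumed at the lower dose, the same toxicity recurs with the same or worse severity", with the qualifier "except for thrombocytopenia, anemia, and neutropenia".

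Related provisions:

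- Section 5.1.3 allows reductions one level at a time: "Dose reductions more than one level at a time will not be allowed, except for thrombocytopenia". It also sets the floor: "If a patient cannot tolerate dose level (-1), then he/she must be discontinued from study medication and withdrawn from the study". Level (-1) is 5 mg once daily.
- Table 5-4, from Day 29, has a related grade 2 hemorrhagic event held until resolved and then restarted one level lower.
- The last paragraph of 5.1.4 sends platelet and ANC declines after a restart back to Table 5-4 for a new lower dose or an interruption.
- Section 6.1.4 has a separate platelet stop for counts below 25 x10^9/L "while taking INC424 at 5mg qd".

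Section 5.1.4 refers to 6.1.4 only for follow-up of patients who discontinue. The toxicity list in 6.1.4 refers to Section 5.1.2.8 and Table 5-4, not to the recurrence sentence in 5.1.4. The Amendment 4 rationale describes 6.1.4 as compiling criteria already in the protocol, with none added. That is not a precedence rule. The SAP has no discontinuation rule that settles the matter.

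**The concern.** The same clinical course can end treatment under one section and not yet trigger a stop under the other. Section 6.1.4 is presented as the complete list of stopping criteria, so a site could reasonably work from it and from Table 5-4, and give drug again where 5.1.4 requires a stop.

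The case that matters most is recurrent bleeding. Hemorrhagic events are a named focus of the safety endpoint (Section 2.2), and every patient enters with platelets below 100 x10^9/L. Whether drug is given again after a second related grade 2 bleed should not depend on which section a site opens. The choice also affects who is counted in the SAP tables of adverse events leading to discontinuation or dose adjustment (SAP 2.3.2). It can affect who is recorded as a protocol deviation (SAP 2.2.5), because Section 11 of the protocol permits no authorized deviations.

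**Working it through.** The plan gives no figure to reproduce. The check sets the two rules side by side and steps through the dose ladder.

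**Inputs.** The permitted total daily doses are 5 mg (level -1, Section 5.1.3) and 10, 15, 20, 25 and 30 mg (Table 5-2). Each event is a related, non-cytopenic toxicity of the same grade that Table 5-4 holds and restarts one level lower. An event at level (-1) leads to a stop, because no lower dose is allowed.

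**Event at which stopping becomes mandatory, no earlier reduction:**

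| Dose at event 1 (mg/day) | Path under 6.1.4 with Table 5-4 | 5.1.4 | 6.1.4 with Table 5-4 | Extra re-exposure (mg/day) |
|---|---|---|---|---|
| 5 | none lower | 1 | 1 | none |
| 10 | 10, 5 | 2 | 2 | none |
| 15 | 15, 10, 5 | 2 | 3 | 5 |
| 20 | 20, 15, 10 | 2 | 3 | 10 |
| 25 | 25, 20, 15 | 2 | 3 | 15 |
| 30 | 30, 25, 20 | 2 | 3 | 20 |

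The rules differ at 4 of 6 steps, by one further re-exposure each time.

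**Worked case.** A patient on 10 mg b.i.d., with no earlier reduction and platelets at or above 50 x10^9/L throughout, has a related grade 2 bleed after Day 28. Dosing is held and restarted at 15 mg/day. A second related grade 2 bleed follows. Section 5.1.4 requires a stop. The 6.1.4 bullet is not met, since only one reduction has occurred, and Table 5-4 would reduce again to 10 mg/day. The same gap applies to related grade 2-3 bilirubin with direct bilirubin at or above 0.5 mg/dL, and to grade 3 DLTs in the row for other adverse events.

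**With one earlier reduction for a different toxicity.** If 6.1.4 counts every reduction, the first bleed produces reduction 2 and the second bleed is a stop, so 0 of 6 steps differ. If it counts per toxicity, 4 of 6 differ as above. Section 6.1.4 does not say which.

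**Applying both rules together.** Any patient who meets the 6.1.4 bullet has already had a same-or-worse recurrence after resuming at a lower dose, and so already meets 5.1.4. On this reading, neither the two-reduction threshold nor the exemption ever changes an outcome.

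**Platelets and ANC.** After Day 28 a patient on 10 mg b.i.d. falls below 25 x10^9/L, is held, recovers to at least 50, restarts at 5 mg b.i.d. (Table 5-6), and falls below 25 again. The 5.1.4 sentence, read literally, says stop. Table 5-4 says hold: from Day 29 it holds in 5 of 6 dose columns and discontinues only in the 5 mg qd column.

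**The case against.** The strongest reply is that there is no conflict of duties. Both sentences are conditions for stopping, and nothing in 6.1.4 authorizes continuing. A site that stops at the earlier trigger complies with both. Table 5-4 is titled as recommended modifications and belongs to Section 5.1.4, so a site using the table should meet the stop sentence that follows its introduction. This stands in part. A reader might infer that the two sections order opposite actions, or that the protocol mandates re-dosing after a second bleed. The documents do not support that: at event 2, 6.1.4 is silent. But applying both empties the 6.1.4 bullet. It also forces stops for recurrent platelet and ANC falls that the restart tables manage by hold or reduction.

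Second, the platelet and ANC conflict is largely settled by the last paragraph of 5.1.4 and by Tables 5-4 to 5-6. That stands. Those specific provisions most likely govern, and this part adds little weight.

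Third, 4 of 6 counts rule outcomes, not patients. That stands. The Amendment 4 rationale reports frequent reductions after cycle 1 in Stratum 1 patients starting at 15 mg b.i.d., without giving reasons. If 6.1.4 counts every reduction, earlier reductions shrink the gap.

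Fourth, other safeguards exist. Related grade 3-4 bleeds have their own stop, and the investigator should stop treatment "if he/she believes that continuation would be detrimental" to the patient. These limit the harm but do not close the gap. Required sponsor consultation before restart covers DLTs, whose window ends at Day 28, while treatment runs to 3 years. Repeat grade 2 bleeds have no stop of their own.

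**Conclusion.** The inconsistency is real and should be fixed. Two live mandatory rules differ on the number of reductions (one versus two) and on exemptions (none versus three cytopenias), with no precedence text. It matters most for hemorrhagic and other non-hematologic toxicity that is held and restarted one level lower. There, with a first event at 15 to 30 mg/day and no earlier reduction, reliance on 6.1.4 with Table 5-4 allows one more re-exposure than 5.1.4 does.

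This rests on one-level reductions per event and on an event at level (-1) ending treatment. The number of patients affected cannot be derived from the documents. A reader might also infer a threat to the primary analysis. The documents do not support that, because only DLTs through Day 28 enter the dose-finding model, so the DLT/MSSD analysis is largely unaffected.

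**What to change.** State one rule in both sections.

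1. **Section 5.1.4.** Take thrombocytopenia and neutropenia out of the recurrence stop and refer them to Tables 5-4 to 5-6. Keep the existing separate stops: platelets below 25 x10^9/L at 5 mg qd, and a second episode of grade 3 or higher febrile neutropenia. Carry over the 6.1.4 exemption for anemia only with a stated handling rule, for example the row for other adverse events in Table 5-4. That table has no anemia row, so a bare exemption would leave anemia with no named handling.
2. **Section 6.1.4.** For hemorrhagic and other non-hematologic toxicity, use the stricter trigger already in 5.1.4: stop at the first same-or-worse recurrence after one reduction. If the sponsor documents that two reductions were intended, both sections should say two and state whether reductions are counted per toxicity.

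Section 11.1 requires a written protocol amendment, so a clarification letter is not enough. The text change is small: one sentence in 5.1.4, one bullet in 6.1.4 and a line for anemia, with no change to data collection or analysis. The downside of the stricter trigger is that some patients, number unknown, may stop one dose level earlier.
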